A retrospective cohort data linkage study of patients aged 18 years and above registered in English general practices. This protocol is written following RECORD guidance [12].

Settings Describe the setting, locations, and relevant dates, including periods of recruitment, exposure, follow-up, and data collection.

1205 general practices in England contributing to the QResearch database, which is nationally representative. We defined cohorts during the COVID pandemic as between 24th January 2020 (the date of the first confirmed COVID-19 case in England) and study end (30th June 2021). We defined retrospective comparison cohorts as the 5 years prior to this date (24th January 2015- 23rd January 2020).

Data linkage

The study will include adult patients registered with the QResearch database. Practices must have been contributing to the QResearch database for at least 12 months. For the investigation of associations of pre-existing neuropsychological diseases and treatments (cohort 1) patients must be registered for at least a 12-month period before 24th January 2020. For the investigation of incidence of new neuropsychological diseases (cohort 2) patients must be registered for at least a 12-month period between January 2015 to 2020. The date of study entry is separately defined below for each study cohort.

Patients in QResearch will be linked to: (1) the ICNARC Case Mix Programme (CMP) database, the national clinical database from adult critical care; (2) the Hospital Episode Statistics (HES) data warehouse containing records of all patients admitted to NHS hospitals and Emergency departments in England; (3) the national registry of COVID-19 RT-PCR positive test results from Public Health England (PHE); and (4) Office of National Statistics COVID-19 mortality data, which includes all deaths due to COVID-19 in England. Data linkage will be based primarily on NHS number. For a description of the datasets see Supplemental material S1.

Participants

Give the eligibility criteria, and the sources and methods of selection of participants. Describe methods of follow-up. The methods of study population selection (such as codes or algorithms used to identify subjects) should be listed in detail.

Aim 1.

From the linked dataset, we will extract two cohorts to explore the association between neuropsychological diseases and treatments and hospitalisation, ICU admission or death:

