 Cohort one is adult patients aged 18 years of age or over on 24th January 2020 (the study entry date, when the first confirmed COVID-19 case occurred in the UK) who were registered in a primary care practice within the QResearch programme on or before 24th January 2019. Patients will be followed-up from study entry date until development of severe COVID-19 disease, defined as the first date of either hospitalisation, ICU admission, or death. Patients will be censored at the first occurrence of deregistration from the GP practise, death, or date of the final data extract from the linked datasets.

Cohort two is an open cohort of patients aged 18 years of age or over (including those who become 18 within this period) who had been registered with a primary care practise within the QResearch database for at least one year, between 24th January 2015 and 23rd January 2020. For each patient, the earliest day on which all these conditions were met will be defined as their study entry date, and they will be followed-up until development of severe disease due to SARI, defined as hospitalization, ICU admission, or death. Patients will be censored at the earliest of first occurrence of deregistration from the GP practise, death from other causes, 24th January 2020 or date of the final data extract from the linked datasets.

Aim 2.

- Cohort three will include adult patients (aged 18+ on date of hospital admission) discharged alive following a hospital admission including an ICU admission resulting from COVID -19 infection (defined below) between 24 January 2020 and study end date, who were registered in a primary care practice within the QResearch programme before their ICU admission. It will be used to evaluate the risk of subsequent neuropsychological sequalae from the date of discharge. Patients will be censored at the earliest of first occurrence of deregistration from the GP practice, death from other causes, 12 months post discharge from hospital, or date of the final data extract from the linked datasets.

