- Cohort four will include adult patients (aged 18+ on date of hospital admission) discharged alive following a hospital admission including an ICU admission resulting from SARI (defined below) admitted between 24 January 2015 and 23rd January 2020, who were registered in a primary care practice within the QResearch programme before their ICU admission. The cohort will allow comparisons to be made with cohort three. Follow-up will be from the date of discharge. Patients will be censored at the earliest of first occurrence of deregistration from the GP practise, death from other causes, 12 months post discharge from hospital or date of the final data extract from the linked datasets.
- Cohort 5 will include adult patients (aged 18+ on date of hospital admission) discharged alive following a hospital admission including an ICU admission resulting from SARI (defined below) between 24 January 2020 and study end date, who were registered in a primary care practice within the QResearch programme before their ICU admission. It will be used to allow comparison with cohort 3. Patients will be censored at the earliest of first occurrence of deregistration from the GP practice, death from other causes, 12

months post discharge from hospital, or date of the final data extract from the linked datasets.

Variables

Definition of outcomes Aim 1

For cohort one, our primary outcome is the first occurrence of any one of the following:

1. Hospital admission resulting from COVID-19 infection defined as testing positive for SARS-CoV-2 (as recorded in the PHE database) in the 14 days prior to or during a hospital admission period in the HES dataset, or having an ICD10 code U07.01 for confirmed COVID-19 diagnosis in that HES admission record

2. Admission to an ICU resulting from COVID-19 infection which will be defined as patients admitted to an ICU within the ICNARC dataset of COVID-19 admissions.

3.All - cause mortality following COVID-19 infection.

Secondary outcomes are each of the three events defined above, considered separately (i.e. COVID-19 hospital admissions; ICU admission; death).

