For cohort two, our primary outcome is the first occurrence of either hospital admission with SARI in the HES dataset (defined as a new ICD-10 code J09-J22 in the HES dataset) or ICU admission in the ICNARC CMP dataset with SARI (defined as any admission with unique diagnostic code any one of RE129 RE131 RE82 RE50 RE86 RE94 RE75 RE133 RE132 RE121 RE1 RE128 RE16 RE130 RE117 RE42 RE41) or death. Secondary outcomes will be each of these three events considered separately (I.e. SARI related hospital admission, ICU admission, death).

Aim 2.

Our primary outcome is development of new neuropsychological disease up to 1 year following hospital discharge which we define as having received a diagnostic code as below:

- Anxiety and stress-related disorders [ICD F40-48 and corresponding Read codes]
- Mood disorders [ICD F30-39 and corresponding Read codes]
- Psychotic disorders [ICD F20-29 and corresponding Read codes]
- Dementia [ICD F00-F03, G30, G31.0 ? and corresponding Read codes]

Secondary outcomes are the diagnosis of new neuropsychological disorders (as defined above) with treatment, and where numbers are available the new diagnosis with or without treatment of each class of disorders, each considered as a separate endpoint.

Neuropsychological treatments are defined as:

- Hypnotics and anxiolytics: (hypnotics, anxiolytics, barbiturates and methyprylone, benzodiazepines)
- Antidepressant drugs (Tricyclic and related antidepressant drugs, Monoamine-oxidase inhibitors, Selective serotonin re-uptake inhibitors, Other antidepressant drugs)
- Drugs used in psychoses and related disorders (Antipsychotic drugs and depot injections, Lithium salts, Phenothiazine derivatives)

Definition of exposures

Aim 1

Neuropsychological disease will be defined as an ordinal variable with the following three categories: no relevant diagnosis or drugs; diagnosis ever recorded without recent drug treatment; diagnosis present with recent drug treatment (with at least two prescriptions for neuropsychological treatments as above within the six months preceding study entry).

Our primary exposure is active neuropsychological disease on the study entry date which we define as having received a diagnostic code as above (24th January 2020 for cohort 1 and 24th January 2015 for cohort 2).

Aim 2.

The primary exposure is a hospital or ICU admission resulting from COVID-19 infection. Comparator exposures are hospital or ICU admission resulting from SARI.

Covariates

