Sensitivity analyses

We will undertake complete case analysis in those without missing data as a sensitivity analysis of our findings.

We will also restrict analysis to only include patients with confirmed COVID-19 diagnosis using RNA testing.

For Aim 2 we will carry out a sensitivity analysis in cohort four with additional censoring of follow-up on 24th January 2020, so that outcomes are assessed prior to the pandemic period. In comparing cohort 3 and 4 we will consider the competing risk of death by undertaking a competing risk analysis.

In order to compensate for the low expected event rates relative to our sample sizes for aim 2, we will combine cohorts 3 and 4 and use all available baseline characteristics (as listed previously) to calculate a propensity score to measure the likelihood of developing a new neuropsychological condition up to 1 year after ICU admission. We will then use these scores (with inverse probability weighting) to compare the adjusted hazard of developing a new neuropsychological condition in patients admitted to critical care for COVID compared to those admitted for SARI.

The authors will have full access to anonymised data from the Case Mix Programme, QResearch and Public Health England, and Hospital Episode statistics databases. We will remove duplicate records for the same individual, and set dates and values outside a pre-defined credible range as missing. For patients admitted with SARI between 2015-2020 the full set of standard data validation processes for unit level data intended for public reporting will have been carried out by ICNARC. Some of the more recent Covid admissions will have undergone a more restricted set of validations, but these do include confirming the total number of admission with Covid to each unit, checking that duration of organ support does not exceed duration of stay, and confirming with units that that aggregated units level summaries of length of stay and organ support (among other measures) are in line with expectations. All variables used in the analysis will be initially summarised in a table of baseline characteristics to include minimum, maximum, median and quartiles.

Data linkage

Person-level data linkage will be undertaken between QResearch, Hospital Episode Statistics, the Case Mix Programme and Public Health England. Cases will be matched on pseudonymised NHS number [15].

Discussion

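### SARI follow-up in cohorts 4 and 5 is not ended by a later COVID-19 admission and the Aim 2 cohorts can overlap, so one diagnosis can count in both arms; this matters mainly for cohort 5

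*Protocol*

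**What the plan says.** All references are to the Protocol.

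- **Participants, Aim 2, cohort 4.** SARI patients "admitted between 24 January 2015 and 23rd January 2020, who were registered in a primary care practice" are followed from discharge. The censoring rule reads "Patients will be censored at the earliest of first occurrence of deregistration from the GP practise, death from other causes, 12 months post discharge", with the final data extract as the last item.
- **Participants, Aim 2, cohort 5.** These are patients with an ICU stay "resulting from SARI (defined below) between 24 January 2020 and study end date". The censoring events are the same four. Of its purpose the protocol says "It will be used to allow comparison with cohort 3".
- **Participants, Aim 2, cohort 3.** Entry is for adults "discharged alive following a hospital admission including an ICU admission resulting from COVID -19 infection (defined below) between 24 January 2020 and study end date". An earlier SARI admission is not an exclusion.
- **Bias.** Cohort 5 is presented as the same-period comparison that answers the problem of cohorts 3 and 4 being observed in different years.
- **Statistical Methods, Aim 2.** The model written out compares cohort 3 with cohort 4. Its only clustering term is a frailty for critical care unit.
- **Sensitivity analyses.** For cohort 4 only, the protocol plans "additional censoring of follow-up on 24th January 2020, so that outcomes are assessed prior to the pandemic period".
- **Participants, Aim 1.** The Aim 1 SARI cohort (cohort 2) is censored at 24 January 2020 in its main analysis.

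**The concern.** The censoring list is closed and omits the exposure under study. A SARI survivor who then has COVID-19 within the year stays at risk in the SARI arm, and a diagnosis made after the COVID-19 illness is credited to SARI. If that illness includes an ICU stay and the patient is discharged alive, the patient also enters cohort 3. The same first diagnosis is then an event in both arms. The critical care unit frailty does not deal with one person appearing on both sides of the contrast. The planned removal of duplicate records for an individual does not deal with it either, since two genuine admissions are not duplicates.

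At stake is the hazard in the SARI arm, and above all in cohort 5. The comparison offered as the safeguard against period bias is the one most open to contamination by COVID-19. The calendar cut-off planned for cohort 4 cannot be carried over, because it would remove all of cohort 5's follow-up.

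The point is about what happens after entry to a SARI cohort. How a single admission coded as both SARI and COVID-19 is classified is a separate question.

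**Working it through.** The protocol gives no effect size, power or event count for Aim 2, so there is no planned figure to reproduce.

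**Inputs from the protocol.** Cohort 4 admissions run from 24 January 2015 to 23 January 2020 (1,826 days). Follow-up is at most 12 months. Expected sizes are about 11,000 (cohort 3), 7,000 a year or 35,000 over five years (cohort 4), and 3,500 (cohort 5).

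**Assumptions, not in the protocol.** Admissions are uniform over time, and discharge is taken at admission. A proportion *q* of SARI survivors with follow-up in the pandemic have COVID-19 during it, at uniform times. The range for *q* is 5–20% in cohort 5 and 2–20% in cohort 4.

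**Step 1. Share of follow-up in the pandemic.** In cohort 4, patients admitted in the last 364 of 1,826 days have some follow-up after the cut-off: 364/1,826 = 19.9%, about 7,000 of 35,000. On average half of their year falls there, so about 10.0% of person-time is exposed (11.1% with a 20-day stay). In cohort 5 it is 100%.

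**Step 2. Share of SARI person-time after COVID-19.** *f* = pandemic share × *q* × 0.5.
- Cohort 5: *f* = 2.5% (*q* = 5%) to 10% (*q* = 20%).
- Cohort 4: *f* = 0.1% (*q* = 2%) to 1% (*q* = 20%).

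**Step 3. Effect on the hazard ratio.** Observed HR = HR / (1 − *f* + *f k*), where *k* is the post-COVID hazard relative to the SARI hazard.

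(a) Every infection carries the full hazard of the COVID-19 arm (*k* = HR), with a true HR of 1.5:

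| Comparator | *q* | Observed HR |
|---|---|---|
| Cohort 5 | 5% | 1.5/1.0125 = 1.481 |
| Cohort 5 | 10% | 1.5/1.025 = 1.463 |
| Cohort 5 | 20% | 1.5/1.05 = 1.429 |
| Cohort 4 | 2% | 1.5/1.0005 = 1.499 |
| Cohort 4 | 20% | 1.5/1.005 = 1.493 |

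On the log scale, ln 1.5 = 0.405. Cohort 5 loses ln 1.0125 = 0.012 to ln 1.05 = 0.049, or about 3–12%. Cohort 4 loses at most 0.005.

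(b) Only admitted infections carry that hazard. If one infection in five is admitted (assumed) and the others leave the hazard unchanged, *f* in cohort 5 is 0.5–2%. The HR of 1.5 becomes 1.5/1.0025 = 1.496 to 1.5/1.01 = 1.485, a loss of about 0.6–2.5% of the log HR.

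(c) A second illness doubles the hazard whatever the true HR (*k* = 2, assumed). In cohort 5 with *q* = 5–20%, observed HR = HR/(1 + *f*):
- true 1.5 becomes 1.463 to 1.364;
- true 1.0 becomes 0.976 to 0.909;
- true 0.8 becomes 0.780 to 0.727.

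In the last two the movement is away from 1.

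**Step 4. Scale.** With an assumed event risk of 5–10% in each arm, SE(log HR) = √(1/d₁ + 1/d₂). For cohort 3 versus 5 it is √(1/550 + 1/175) = 0.087 down to √(1/1,100 + 1/350) = 0.061. For cohort 3 versus 4 it is 0.049 down to 0.035.

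**Overlap.** Double counting needs a survived SARI ICU stay, a later survived COVID-19 ICU stay, and a first diagnosis after that, all within 12 months of the SARI discharge. The protocol permits the sequence but gives no figure from which to size it.

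**The case against.** The strongest reply is that the comparison for which a model is written, cohort 3 versus cohort 4, is hardly touched and already has a check. A shift of at most 0.005 in log HR under (a) is small beside a standard error of 0.035–0.049, and the planned cut-off at 24 January 2020 removes essentially all post-COVID time from cohort 4. This stands. A reader might infer that the main Aim 2 result is materially biased; the documents do not support that.

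A reader might also infer that the bias is always toward 1. That follows only if the post-COVID hazard resembles cohort 3's. Calculation (c) shows the HR can be pulled away from 1 when the truth is at or below 1.

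The cohort 5 range of 1.48–1.43 gives a mild community infection the same hazard as a COVID-19 ICU stay. Neither the Aim 2 exposure (a hospital or ICU admission) nor the entry rule for cohort 3 supports treating the two alike. That figure is therefore an upper bound on dilution of this kind, and even at its extreme the shift (0.049) is below one standard error.

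Finally, following patients by index admission, whatever happens later, is a legitimate estimand. Censoring the SARI arm at any positive test is asymmetric, because cohort 3 is not censored at a later SARI or reinfection, and it may be informative. This argues against making test-based censoring the main rule. It does not justify letting one diagnosis count in both arms. A SAP may well add detail on assigning patients, but the protocol itself fixes the censoring list and the entry rules, and as they stand they allow the overlap.

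**Conclusion.** The point holds, with its weight on cohort 5 and on the overlap between cohorts. As written, the rules allow a SARI survivor later treated in ICU for COVID-19 to be at risk in both arms, and nothing planned prevents this for cohort 5.

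The likely distortion of the cohort 3 versus 5 hazard ratio is modest. It depends on an infection proportion, and on a hazard after COVID-19, that the protocol does not give. Its direction is not fixed in advance, and the extent of double counting cannot be estimated from the documents. The error is nonetheless systematic and avoidable, and it falls on the comparison meant to answer period bias. Severity is minor to moderate.

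**What to change.** 1. **Main rule, cohorts 4 and 5.** Add to the censoring list the first COVID-19 admission that qualifies the patient for cohort 3. From that discharge the patient contributes to cohort 3 only. Time before the admission stays with SARI, the stay itself belongs to neither arm, and no diagnosis counts twice.
2. **Sensitivity analysis, cohort 5.** Censor follow-up at the first positive SARS-CoV-2 test or COVID-19 admission, as a counterpart to the calendar cut-off planned for cohort 4.
3. **Reporting.** Show the estimate without any COVID-19 censoring alongside, since censoring at infection may be mildly informative.

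The cost is a few lines of text. The dates are in the PHE, HES and ICNARC data that are already to be linked. Under the assumptions above, item 2 removes about 2.5–10% of cohort 5 person-time. Item 1 removes less than that in cohort 5 and at most about 1% in cohort 4, because it acts only on admissions that qualify for cohort 3.

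### The cohort 1 hospital outcome is labelled as caused by COVID-19 but defined by timing alone, so incidental positives in psychiatric or dementia stays can raise the hazard ratio

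*Protocol*

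**What the plan says.** Protocol, Definition of outcomes Aim 1, item 1 of the cohort 1 primary outcome: "Hospital admission resulting from COVID-19 infection defined as testing positive for SARS-CoV-2". The timing condition on that test is that it falls "in the 14 days prior to or during a hospital admission period in the HES dataset". A second route into the outcome rests on coding: "or having an ICD10 code U07.01 for confirmed COVID-19 diagnosis in that HES admission record". The code route is an alternative to the test route, so it does not narrow it, and no diagnosis position is required.

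The Data linkage section describes HES as "containing records of all patients admitted to NHS hospitals and Emergency departments in England". No stay is excluded by specialty or reason for admission.

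The Participants section follows cohort 1 until "development of severe COVID-19 disease, defined as the first date of either hospitalisation, ICU admission, or death".

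Under Definition of exposures: "Our primary exposure is active neuropsychological disease on the study entry date which we define as having received a diagnostic code as above". The codes referred to are those for anxiety and stress-related disorders, mood disorders, psychotic disorders and dementia.

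**The concern.** The label is causal, but the rule only requires that a positive test and a hospital stay overlap. A person admitted for psychosis who tests positive on the ward in week six, without becoming ill from it, meets the primary outcome and is reported as having severe COVID-19. Read literally, the event is then dated at admission, weeks before the infection. If the stay was already open at study entry on 24 January 2020, the event date would precede entry.

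The error need not be the same in the two groups. The exposure is itself a reason for hospital admission. Stays for these conditions hardly occur in people without such a diagnosis at entry, the exception being diagnoses made later. Incidental positives in those stays therefore add events almost entirely to the exposed group. Part of the primary hazard ratio could then reflect psychiatric and dementia bed use, not severe COVID-19.

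**Working it through.** **Does anything else in the Protocol repair it?**

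- Sensitivity analyses: restricting to RNA-confirmed infection keeps incidental and hospital-acquired positives, because these are RNA-confirmed too.
- Bias: the text deals with testing bias and with differing exposure to infection by condition. It does not deal with reason for admission. The condition-specific analyses it adds use the same outcome.
- Secondary outcomes: ICU admission and death are also analysed separately. This leaves the primary composite and the hospital component unchanged.
- Cohort 2: the hospital outcome is a new code J09–J22 with no test-during-stay route. Diagnosis position is not stated there either.

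**Direction and size.** The Protocol gives no event rates, no share of incidental positives and no expected hazard ratio, so there is no figure to reproduce. All inputs below are assumptions. The algebra treats the hazard ratio as a ratio of event rates.

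*A. Stays for the psychiatric condition or dementia itself, exposed group only.* Let f1 be the share of counted exposed events that are non-severe incidental positives in such stays. Genuine exposed events are then (1 − f1) of those counted, so

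HR observed = HR true / (1 − f1).

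| f1 | HR true 1.00 | HR true 1.20 |
|---|---|---|
| 1% | 1.00/0.99 = 1.01 | 1.20/0.99 = 1.21 |
| 5% | 1.00/0.95 = 1.05 | 1.20/0.95 = 1.26 |
| 10% | 1.00/0.90 = 1.11 | 1.20/0.90 = 1.33 |

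The shift is upward for every f1 above zero.

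*B. Incidental positives in stays for other reasons, both groups.* Let f0 be the share of counted unexposed events that are incidental, and R the exposed-to-unexposed rate ratio of incidental-positive stays. Then

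HR observed = (1 − f0) × HR true + f0 × R.

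With f0 = 10%:

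- HR true 1.00, R = 1.5: 0.9 × 1.00 + 0.1 × 1.5 = 1.05
- HR true 1.00, R = 3: 0.9 × 1.00 + 0.1 × 3 = 1.20
- HR true 1.20, R = 1: 0.9 × 1.20 + 0.1 × 1 = 1.18
- HR true 1.20, R = 3: 0.9 × 1.20 + 0.1 × 3 = 1.38

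The observed ratio exceeds the true one only when R > HR true. In the third case the bias is towards the null.

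**Precision.** The Study Size section gives about 8.3 million adults for Aim 1. In a cohort of that size, a bias of several per cent is unlikely to be hidden by sampling error.

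**The case against.** A sponsor could fairly make four points.

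- **Estimand.** Aim 1 deliberately analyses the whole eligible population, not only those who test positive, and the Bias section accepts that conditions differ in exposure to infection. The hazard ratio therefore includes the risk of acquiring infection, and catching it in hospital is one route. This stands: a severe hospital-acquired infection is not in itself a misclassified event. Only non-severe incidental positives are.
- **Other outcomes give a check.** ICU admission comes from the ICNARC dataset of COVID-19 admissions and does not use the HES test window. A hospital hazard ratio out of line with those for ICU admission and death would be visible. This stands in part: it could raise suspicion but would not correct the primary composite.
- **Cancellation against SARI.** Cohort 2 is not limited to primary diagnoses either, so some of the bias may cancel in objective 3. This is possible there, but it does not help the cohort 1 hazard ratio itself.
- **This belongs in an analysis plan.** Sensitivity analyses often do. The outcome rule and its label, however, are fixed in the Protocol, and they disagree.

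A reader might also infer that the rule inflates the hazard ratio generally and by a large amount. For example, assume incidental shares of 10% in the unexposed and 20–30% in the exposed. Then HR observed = HR true × 0.9/0.8 to HR true × 0.9/0.7, which is 1.125–1.29 from 1.00 and 1.46–1.67 from 1.30. The documents do not support this. The shares appear nowhere, and they imply R = f1 × HR observed / f0, where f1 is here the exposed share. That gives 2.25 and 3.9 for a true ratio of 1.00, and 2.9 and 5.0 for 1.30. Those ratios would have to hold after adjustment for age, domicile, household size, deprivation and a long list of comorbidities. Upward bias from general medical or surgical stays is conditional, as part B shows.

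**Conclusion.** The point holds in a limited form. The hospital component is named as a consequence of COVID-19 but defined only by timing, and its date can precede the infection. Upward bias follows from the design for non-severe incidental positives in stays for the psychiatric condition or dementia. It assumes only that such stays are rare in people with no diagnosis at entry. For other stays the direction depends on whether R exceeds the true hazard ratio.

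The size cannot be derived from the Protocol. As an assumed range, if these psychiatric and dementia stays are 1–10% of exposed events, a true hazard ratio of 1.00 is observed as 1.01–1.11. That may be trivial, or it may be enough to create an apparent weak association. The effect of the event dating on the hazard ratio has not been quantified and is probably the smaller issue.

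**What to change.** Keep the main rule. For the primary composite and for the hospital outcome, pre-specify two separate sensitivity analyses:

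- **(a)** Count only hospital admissions with COVID-19 as the primary diagnosis. This removes admissions for psychiatric or other reasons with an incidental positive.
- **(b)** Exclude stays whose first positive test falls after a pre-stated early day of the stay. The documents offer no basis for a particular day, so the cut-off is an assumption to be justified. State how stays identified by code alone, without a PHE test date, are handled.

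The two should not be joined by an either/or rule, because a psychiatric admission positive on the day of arrival would then still count. In the composite, ICU admissions and deaths should remain events under both, so that severe hospital-acquired infection is kept.

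In all analyses, date an event whose first positive test follows admission at the test date. Tabulate by exposure group the share of events first positive after the chosen day and the share with a primary psychiatric or dementia code. That table would show whether the problem is negligible or material.

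The cost is small: PHE test dates and HES admission records are already to be linked, assuming that the HES extract carries diagnosis position. The downside is that some genuine late-tested or secondarily coded COVID-19 admissions are lost from the sensitivity analyses.
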